each Institution's standards of care. In the PJ Group, the amylase value of drain fluids will be checked on POD1, POD3 and at any POD if it will help to diagnose a still undiscovered POPF. Surgical drain will be managed according to clinical judgment and each Institution's clinical standards. During hospitalization, all patients will receive specialistic evaluation to assess and possibly treat the occurrence of new onset diabetes or the worsening of pre-existing diabetes. Pancreatic exocrine insufficiency will be treated with oral supplementation of pancreatic enzymes if needed. Patients in the TP Group will be vaccinated 1 month after complete functional recovery against Pneumococcus, Hemophilus influenzae group B, and Meningococcus to minimize the likelihood of developing post-splenectomy sepsis. All patients will receive an outpatient follow-up, 1 month after discharge and every 6 months for 2 years. During follow-up, glycemic control, nutritional status, and possible symptoms of exocrine insufficiency will be assessed, and patients will receive specialistic assistance if needed. QoL will be registered using specific questionnaires. An oncologic evaluation will determine the indication for administration of adjuvant therapy, in case of malignancy.

Questionnaires

All patients who will be alive after at least 12 months of follow-up will be enrolled in the cross-sectional study of quality of life. All the eligible patients who are not able to attend outpatient visits will be contacted by telephone before receiving the 5 questionnaires by mail. Patients who will not respond within 1 month will be contacted again by telephone. Four questionnaires will be administered: (1) the EuroQoL Group questionnaire (EQ-5D); (2) the European Organization for Research and Treatment of Cancer (EORTC) QLQ-C30 questionnaire; (3) the European Organization for Research and Treatment of Cancer (EORTC) QLQ-PAN26 questionnaire; and (4) the Problem Areas in Diabetes (PAID) questionnaire.^{17 18 19 20} The comprehensive assessment will consist of a total of 116 questions.

ENDPOINTS

Primary endpoint

For each study group the primary endpoint is the rate of postoperative major morbidity, defined as Clavien-Dindo ≥ 3 .

Secondary endpoints

For each study group secondary endpoints are:

- Incidence of In-hospital, 30-days and 90-days postoperative mortality. Beyond these time-limits, the mortality that may be related to the operation will be considered and discussed in each case.

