- Incidence, severity, and overall average complication burden for PPH and DGE
- Incidence of other postoperative morbidity (see below)
- Time-to-functional recovery (functional recovery is defined by all of the following criteria: adequate pain control with only oral analgesia (no intravenous or epidural analgesia necessary); independent mobility; ability to maintain more than 50% of the daily required caloric intake; no need for intravenous fluid administration; and no signs of infection)²¹
- Length of hospital stay
- Postoperative endocrine insufficiency (new onset diabetes, worsening of pre-existent diabetes, insulin dependency). The definition of postoperative new onset of diabetes will be based on the reporting of a normal preoperative FBG/HbA1c and postoperatively by measured glucose metabolism including FBG/HbA1c level and/or insulin medication.
- Postoperative exocrine insufficiency (incidence of diarrhea, prescription of pancreatic enzymes, number of capsules). The definition of postoperative exocrine insufficiency will be based on FE-1

determination, the presence of steatorrhea and necessity of enzyme treatment with cessation/mitigation of diarrhea after enzyme supplementation.

- Access to adjuvant chemotherapy (when indicated)
- Delay in starting adjuvant chemotherapy, calculated as the time between surgery and the beginning of adjuvant chemotherapy (when indicated)
- General, cancer-specific, pancreas-specific and diabetes-related QoL (EQ-5D; EORTC QLQ C30 and PAN26; PAID) ^{17 18 19 20}

The observation period for postoperative morbidity will last until the complete recovery from surgery.

Morbidity will include:

- PPH as defined by ISGPS ²²
- DGE as defined by ISGPS ²³
- Bile leakage as defined by ISGLS²⁴
- Enteric fistula defined as presence of enteric fluid from drains, possibly confirmed by sinogram or plain radiography with oral contrast study
- Abdominal fluid collection defined as any intraabdominal fluid collections larger than 5cm confirmed at imaging
- Abdominal abscess defined as an intraabdominal fluid collection containing gas bubbles and producing clinically relevant signs of infection
- Wound infection as defined by CDC ²⁵
- Blood transfusions defined as the number of packed red blood cells unit transfused after the procedure
- Sepsis ²⁶
- Chyle leak as defined by ISGPS ²⁷
- Gastric venous congestion ¹⁶
- Postoperative liver failure
- Myocardial infarction
- Acute kidney injury
- Pulmonary embolism
- Pneumonia

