- Respiratory distress (defined as the need for mechanic ventilation after surgery)
- Urinary tract infection
- Neurological morbidity (cerebrovascular accidents, hemorrhage)
- Re-operation
- Re-admission within 30, 60 and 90 days

For PA Group additional secondary endpoints are:

- Incidence and severity of POPF ²⁸
- Incidence of biochemical leak ²⁸
- Overall average complication burden for POPF
- Incidence of postoperative pancreatitis ²⁹

SAMPLE SIZE CALCULATION

A recent metanalysis by Schuh et al. reported a POPF rate around 23% in stage D patients (main pancreatic duct diameter ≤ 3 mm, soft pancreas) but no data were available regarding major morbidity¹². Patients that will be considered eligible for the present trial will have further features increasing their risk of POPF and

related major morbidity, compared to stage D patients. Based on the current literature and on a recent retrospective study by the Verona group, considering only a cohort of patients with extremely high FRS (FRS 9-10), the rate of major morbidity can be estimated around 55% after PD and 19% after TP.¹¹

The original risk score proposed in this trial is extrapolated based on previous literature and expert opinions. For this reason, there are no data directly available for estimation of major morbidity in this rare subset of patients, for which we estimate a rate of Clavien-Dindo ≥ 3 of around 40%.

Considering a 1:1 allocation between the groups, a sample size of 49 patients per group would allow a two-sided, two-sample test for binomial proportions to detect a difference in Clavien-Dindo ≥ 3 of 25% (40% vs 15%) with 80% power ($1-\beta$) and an error α of 0,05. The study has a group sequential design allowing for interim analyses at pre-specified timepoints with possible early stopping for efficacy or futility in case of an overwhelming large or small effect, respectively. Considering that extremely high-risk cases represent around 7% of the total amount of PDs performed and that the fistula risk can only be assessed intraoperatively, we expect to approach preoperatively around 1300 patients.

STATISTICAL ANALYSIS

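### Sepsis is observed only until an undefined recovery from surgery, so non-fatal late sepsis, including the post-splenectomy sepsis the protocol links to total pancreatectomy, goes uncounted during 2 years of follow-up

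*Combined protocol and SAP*

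**What the plan says.** Under Secondary endpoints, sepsis (with a cited consensus definition) is one item of the morbidity list. The rule for the whole list is that "The observation period for postoperative morbidity will last until the complete recovery from surgery". No day count or definition is attached to complete recovery from surgery. The only recovery term defined there is functional recovery, whose criteria end with "no need for intravenous fluid administration; and no signs of infection".

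Under Postoperative care, TP patients are to be "vaccinated 1 month after complete functional recovery against Pneumococcus, Hemophilus influenzae group B, and Meningococcus to minimize the likelihood of developing post-splenectomy sepsis". The TP Group section says that the spleen is to be preserved where possible, so not every TP patient will lose it. The expected proportion is not given.

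Follow-up is long: "All patients will receive an outpatient follow-up, 1 month after discharge and every 6 months for 2 years". Its content is set out as follows: "During follow-up, glycemic control, nutritional status, and possible symptoms of exocrine insufficiency will be assessed". Quality-of-life questionnaires and an oncologic evaluation are added, but infection is not mentioned. The Duration and End of the Study section gives quality of life and pancreatic insufficiency as the subjects of the long-term analysis.

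Two other endpoints come close. One is "Re-admission within 30, 60 and 90 days", with no cause required. The other is mortality: deaths beyond 90 days that may be related to the operation are considered case by case.

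**The concern.** The protocol names an infectious harm, links it to one arm and schedules prevention for after functional recovery. It then stops counting that kind of event at a point called recovery. The same patients are seen for two further years, but no listed item would pick the event up.

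The gap may not be neutral between arms. Sepsis early after surgery is where pancreatic anastomosis (PA) is expected to do worse: the retrospective comparison in the introduction reports a rate three times higher after high-risk pancreatoduodenectomy than after TP. Sepsis due to spleen loss is expected mainly in the TP arm. A sepsis result confined to the early window would cover the period in which TP is expected to look better and leave out later, non-fatal cases of a harm specific to TP. What is at stake is the completeness of the harm report for a more extensive operation, not the primary comparison.

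**Working it through.** **1. The plan's own figure.** The claim concerns an observation window, so no sample-size figure depends on it. For completeness, the stated 49 per group reproduces. With 40% against 15%, two-sided alpha 0.05, power 80% and pooled variance under the null:

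n = [1.960 × √(2 × 0.275 × 0.725) + 0.842 × √(0.40 × 0.60 + 0.15 × 0.85)]² / 0.25² = (1.238 + 0.510)² / 0.0625 ≈ 48.9, rounded up to 49. Power at 49 per group is 80.1%. Nothing below changes this.

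**2. Where a late, non-fatal sepsis could be recorded.**

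| Place in the protocol | Time covered | Captures late non-fatal sepsis? |
|---|---|---|
| Morbidity list (Secondary endpoints) | To complete recovery from surgery, undefined | No, once the window has closed |
| Re-admission | To 90 days, any cause | Only as a re-admission, and only to day 90 |
| Mortality beyond 90 days | Open, case by case | No, fatal cases only |
| Outpatient visits (Postoperative care) | 2 years | Infection not listed |
| Long-term analysis (Duration and End of the Study) | Additional 24 months | Quality of life and pancreatic insufficiency only |

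**3. Does the undefined window rescue the plan?** Two readings:

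- If complete recovery from surgery means functional recovery, counting ends when there are no signs of infection, and vaccination comes 1 month later.
- If it means the 3 months of follow-up allowed for the primary endpoint, 24 − 3 = 21 months remain without a sepsis count. That is 21/24 = 88% of calendar time, not of events.

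Only a reading that stretches recovery from surgery to the end of follow-up would close the gap.

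**4. Scale.** The documents give neither the share of TP patients who lose the spleen nor a late-sepsis rate. Both inputs are assumptions: a share of 25%, 50% or 100% of 49 (12, 24 or 49 patients after rounding) and a two-year risk p of 1% to 5%. Expected cases = m × p; chance of at least one = 1 − (1 − p)^m.

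| Splenectomised, m | Expected cases, p = 1% to 5% | Chance of at least one |
|---|---|---|
| 12 | 0.12 to 0.60 | 11% to 46% |
| 24 | 0.24 to 1.20 | 21% to 71% |
| 49 | 0.49 to 2.45 | 39% to 92% |

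**5. Would a formal test help?** Take 3 of 49 against 0 of 49, which is above the top of that range. The chance that all three events fall in one given arm is C(49,3)/C(98,3) = 18,424/152,096 = 0.121, so the two-sided Fisher p is about 0.24. A test would be uninformative; a listing would not.

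**The case against.** The strongest reply is that the timing is inferred. The protocol says when vaccination is given and why; it does not say when post-splenectomy sepsis occurs. Complete recovery from surgery is undefined, is not the same phrase as complete functional recovery, and could run past the vaccination date. Any case inside the window is counted. This stands, and it is why the point is put as a risk that continues after recovery, not as one that begins there. It does not remove the gap, because no ordinary reading of recovery from surgery reaches two years.

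The window is also the same in both arms, and only patients who lose the spleen carry the specific risk. This stands too. The imbalance depends on a splenectomy share that the documents do not give, so the estimate has to allow for spleen preservation and not apply a rate to all 49 TP patients.

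There is partial capture elsewhere: fatal late sepsis has a route through the case-by-case review of deaths, and re-admissions are recorded to 90 days. The case report form is not among the documents, so it may hold more than the listed visit content.

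A reader might go further and infer that late sepsis will be reported as zero in the TP arm, or that the sepsis comparison is one-sided by construction. The documents support neither. Late sepsis is simply not reported, and a result that follows the plan would be limited to the stated period.

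**Conclusion.** The point holds as a gap in harm reporting. As written, the plan does not count non-fatal sepsis after the morbidity window in either arm, although it names post-splenectomy sepsis as a TP-group risk and sees every patient for 2 years. Because spleen loss is expected mainly in the TP arm, the sepsis comparison can miss a harm specific to TP.

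The expected number is small: about 0.1 to 2.5 cases among 49 TP patients, on an assumed splenectomy share of 25% to 100% and an assumed two-year risk of 1% to 5%. The conclusion rests on reading the listed visit content as complete and on inferring from the vaccination schedule that the risk continues after recovery. It is an inexpensive improvement worth making, and no threat to the primary analysis.

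**What to change.** Under Secondary endpoints, keep the early sepsis item as it stands and add wording to this effect: *Spleen status will be recorded for every patient. Sepsis (same definition) and re-admission for infection occurring after the early morbidity window and up to 24 months will be recorded at the scheduled follow-up visits in both arms. They will be reported descriptively by randomised arm, with early and late events shown separately and without a formal test.*

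To make the early/late split reproducible, record the date of each event and the date on which the patient's morbidity window was taken to close. The matching item should be added to the follow-up content under Postoperative care. The Statistical Analysis section, which has all endpoints compared between arms, should state that late sepsis is exempt from testing.

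The cost is one more case-report-form item at visits that already take place. Some recorded events will be unrelated to surgery, for example infections during adjuvant chemotherapy. Access to and timing of that treatment may themselves differ by arm, so the listing should note the circumstances and spleen status of each case. The primary endpoint and sample size are unaffected, and no change to vaccination, surgery or treatment is proposed.

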The operating surgeon will decide whether the patient can be included in the study or must be excluded for the presence of any drop-out criteria (see above). The interobserver agreement of at least another surgeon will serve as a confirmation for the inclusion in the trial (ethical “guarantor”). According to the presence of two major and one or more minor criteria patients will be included in the study and randomized in two groups. A picture of the pancreatic remnant will be taken intraoperatively before anastomosis/totalization. Both patients undergoing open and minimally invasive surgery can be considered eligible.

PA Group

PA will be carried out according to the techniques adopted by the participating Centre, either pancreaticojejunostomy (PJ) (i.e. dunking PJ, Cattel-Warren duct-to-mucosa PJ, Blumgart PJ) or pancreatico-gastrostomy (PG) will be considered eligible. Any mitigation strategy (i.e. ETS, use of glues/biological matrices to protect the anastomosis, surgical feeding jejunostomy, prophylactic hydrocortisone/somatostatin administration) can be used according to the Center practice. The other two anastomosis, hepaticojejunostomy and duodenojejunostomy (in case of Longmire-Traverso PD) or gastrojejunostomy (in case of Kausch-Whipple PD), will be carried out as usual according to each Institution’s operative standards.¹⁵

At least one surgical drain will be placed in the retroperitoneum in all patients.

TP Group

TP will be carried out according to each Institution’s operative standards. Preservation of the spleen will be considered whenever possible according to Kimura technique. Either ligation or preservation of gastric vessels (right/left gastric artery/vein) will be allowed according to clinical necessity but will be recorded and correlated with postoperative outcomes.¹⁶

The reconstruction phase will be carried out according to each Institution’s operative standards. One or more surgical drains can be left in place according to surgeon’s preference.

Postoperative care

After the procedure, the patient will be admitted to the ICU or in the ward. The management of intravenous fluids, nasogastric tube, bladder catheter and postoperative analgesia will take place as usual according to

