Continuous variables will be expressed as the means and standard deviation values or as median values with ranges and will be compared using the Student t-test or the Mann-Whitney test as appropriate. Categorical variables will be analyzed by Chi-square or Fisher's exact test in case of expected small frequencies. All the tests will be 2-tailed. P values < 0.05 will be considered statistically significant. All endpoints will require the above-mentioned statistical analysis, comparing the two study arms. Statistical analyses will be performed using STATA14 for Windows.

DURATION AND END OF THE STUDY

Since the Department of General and Pancreatic Surgery performs about 250 PD per year and the study will be proposed to at least other 2 international referral centers, the primary endpoint will be reached after 25 months: 22 months of patients' enrollment and 3 months of follow-up. Long term analysis of QoL and pancreatic insufficiency will require additional 24 month of follow-up. Time for data analysis must be considered negligible. All the patients undergoing PD will be enrolled for the study if inclusion and exclusion criteria will be respected. The study will be discontinued in case of reaching the statistical significance of the primary endpoint, or in case of suspension by the coordinators or by the authorities.

PROCEDURES RELATED TO REGISTRATION AND DATA MANAGEMENT

To ensure the confidentiality of data, each patient will be registered and de-identified by an identification code.

Each subject will be identified by a code consisting of:

- Code Protocol: TETRIS
- Number of the institution: (e.g. Patient recruited at the Verona Pancreas Institute will be coded as TETRIS_C1)
- Number of recruitment (e.g. the third patient recruited at the Verona Pancreas Institute will be coded as TETRIS_C1_3).

The P.I. of the study will be responsible for data protection and privacy of study participants by treating the data solely for statistical purposes and scientific research, and he will not communicate them if not anonymously. The manager of data processing is the principal investigator.

All data of enrolled patients collected during the study will be recorded in a computerized case report form (CRF) and transferred automatically into a specific database protected by passwords. These data will be kept confidential and will be treated in full compliance with the Legislative Decree 196/03.

ETHICAL CONSIDERATIONS

[figure not shown]

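### Enteric fistula is defined only by enteric fluid from drains, while drains are required under PA and optional under TP, so counting of this secondary item can differ by arm

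*Combined protocol and SAP*

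**What the plan says.** In the protocol's ENDPOINTS section, the morbidity list under Secondary endpoints applies to each study group and includes: "Enteric fistula defined as presence of enteric fluid from drains, possibly confirmed by sinogram or plain radiography with oral contrast study". The list gives no other route to this diagnosis, such as imaging alone, wound output or a finding at re-operation.

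The drain rules are under Procedures, Intraoperative setting. Under PA Group: "At least one surgical drain will be placed in the retroperitoneum in all patients". Under TP Group: "One or more surgical drains can be left in place according to surgeon’s preference". Postoperative care adds: "Surgical drain will be managed according to clinical judgment and each Institution's clinical standards". No minimum duration is set.

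STATISTICAL ANALYSIS then states: "All endpoints will require the above-mentioned statistical analysis, comparing the two study arms".

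The primary endpoint is separate: "For each study group the primary endpoint is the rate of postoperative major morbidity, defined as Clavien-Dindo ≥ 3". It contains no drain criterion.

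**The concern.** Both operations include enteric anastomoses, so an enteric leak can occur in either arm. Whether it counts as enteric fistula depends on a drain being present, and the protocol makes drain placement compulsory under one arm's heading and discretionary under the other's. The rule as written therefore allows detection to differ by arm, without any error by investigators.

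The direction is predictable. If some TP patients have no drain, some TP leaks fail the definition, and the TP rate comes out too low relative to PA. The trial asks whether TP is superior, and comparing complications in each group is a stated secondary objective. A lower enteric fistula rate after TP could then partly reflect fewer drains rather than fewer leaks.

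**Working it through.** **The plan's own figure.** SAMPLE SIZE CALCULATION gives 49 per group for 40% vs 15%, two-sided alpha 0.05 and 80% power. The two-proportion formula with pooled variance and no continuity correction returns 49 per group, with power 0.801. This figure concerns the primary endpoint only and does not change here. The documents give no enteric fistula rate and no drain use in the TP arm.

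**The definition applied to possible cases.** These are illustrations; the documents do not say how common each is.

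| Leak | Counted as enteric fistula? |
|---|---|
| PA, drain in place, enteric fluid in it | Yes |
| PA, leak appears after drain removal, no new drain | No |
| TP, drain in place, enteric fluid in it | Yes |
| TP, no drain, leak seen only on contrast imaging | No |
| TP, no drain at first, later drain yields enteric fluid | Yes |
| TP, no drain, leak found at re-operation, no enteric fluid from any drain afterwards | No (recorded as re-operation) |

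**Size, under assumptions.** Let p be the true leak rate, equal in both arms; u the share of TP patients without a drain; and c the share of undrained leaks that are still counted because a later drain shows enteric fluid. Assume that every leak in a drained patient is counted.

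- Counted rate in PA = p
- Counted rate in TP = p × [1 − u(1 − c)]

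With p = 6% (assumed) and 49 patients per arm, PA has 49 × 0.06 = 2.94 expected counted events. For TP:

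| u | c | TP counted / true | TP rate | TP events per 49 |
|---|---|---|---|---|
| 20% | 0 | 0.80 | 4.8% | 2.35 |
| 20% | 50% | 0.90 | 5.4% | 2.65 |
| 50% | 0 | 0.50 | 3.0% | 1.47 |
| 50% | 50% | 0.75 | 4.5% | 2.21 |
| 80% | 0 | 0.20 | 1.2% | 0.59 |
| 80% | 50% | 0.60 | 3.6% | 1.76 |

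If u = 0 or c = 1, the ratio is 1 and there is no bias.

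**Relaxing full detection in drained patients.** If only a share d of leaks is counted in drained patients of either arm, because drains come out early, the artificial gap becomes p × u × (d − c). With p = 6%, u = 50%, d = 1 and c = 0 this is 3.0 percentage points, as in the table. The gap shrinks as d falls and vanishes when d = c.

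**Chance of a false significant result.** The plan prescribes Fisher's exact test for small expected frequencies. With 49 per arm, true counted rates of 6% and 3% give p < 0.05 in about 2% of trials; 6% and 1.2% give about 4%. A split of 5 events against 0 has p = 0.056.

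**The case against.** The strongest counter-argument is that this is small and unproven. Enteric fistula is one of about 20 items listed as other morbidity, and it is not among the pancreas-specific complications named in the secondary objectives. The definition does not restrict itself to the operative drain, so drains placed later also qualify, and observation runs until complete recovery. PA drains may be removed before a leak appears. An undrained leak may still be recorded as a fluid collection, abscess, sepsis or re-operation. Nothing shows that TP patients often go without a drain, and every rate used above is an assumption.

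Most of this stands, and it limits the point to misclassification of one item. It does not remove the asymmetry. A complication filed under another label still distorts the enteric fistula comparison. The alternative labels also have thresholds: a collection must exceed 5 cm, and an abscess needs gas bubbles and signs of infection, so a small contained leak may meet neither.

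Three stronger readings are tempting. A reader might infer that every PA leak is counted while undrained TP leaks are simply lost; later drains, locally decided drain removal and the other morbidity items contradict this. A reader might infer that the primary comparison is biased; its definition contains no drain element. A reader might also expect a spurious significant difference; the Fisher calculation makes that unlikely, although the descriptive rates could still mislead.

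Finally, the PA drain sentence speaks of all patients and could have been meant for both arms. Its position under PA Group, with a separate permissive sentence under TP Group, makes the narrower reading the natural one. If both arms were meant, the two sentences conflict.

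**Conclusion.** The point holds as a modest weakness in one secondary item. As written, the definition depends on a drain, the drain rule differs by arm, and the item is compared between arms, so detection can differ in favour of TP.

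The size cannot be derived from the documents. With an assumed true rate of 6% in both arms, full detection after PA, half of TP patients undrained, and none to half of their leaks counted later, 2.9 events would be expected in PA against 1.5 to 2.2 in TP per 49 patients: a shortfall of roughly one event. It is zero if every TP patient is drained. The primary endpoint's definition and the sample size of 49 per group are unaffected. The change is worth making because it is cheap and removes the definition's dependence on a drain.

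**What to change.** Use one drain-independent definition in both arms, for example: enteric fluid from any surgical or percutaneous drain or from the wound, or contrast extravasation on imaging, or a leak found at re-operation.

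Make sure the case report form records, in both arms, whether a surgical drain was placed and the date it was removed. The form is not among the documents, so these fields may already exist.

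The cost is one reworded sentence and at most two data fields. No extra procedures are needed, since the definition uses imaging and re-operations done for clinical reasons. The counted rate may rise slightly in both arms. Differences between arms in how often imaging is done could still affect detection.

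No change to drain practice is proposed. If the PA drain sentence was meant to cover both arms, the sponsor must reconcile it with the TP sentence.
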